### **3.2 Rationale for Study Design**

*Study population:* To date, four Phase I trials have been or are currently being conducted to assess the safety, tolerability, and pharmacokinetics of deferiprone delayed release tablets in healthy volunteers. This study will be the first to look at the DR formulation in the population for which it is intended. It is possible that the rates of adverse events that were seen in healthy subjects would occur at different rates in patients, due to the different action of an iron chelator in iron-overloaded vs. non-iron-loaded recipients.

*Dosages:* Patients with systemic iron overload are usually prescribed deferiprone at a dosage ranging from 75 mg/kg/day to 100 mg/kg/day. Dosages within both the upper half and the lower half of this range will be investigated, to determine if there is a dose effect on the adverse events that were seen in healthy subjects (due to tailoring of dosages to individual patient needs and to rounding, most potential subjects will not be on a dosage of Ferriprox that is exactly 75 mg/kg/day or exactly 100 mg/kg/day). In all cases, the total daily dosage of deferiprone DR will be made to match that of Ferriprox IR as closely as possible. Since dosages will be rounded to the nearest 500 mg and body weights of participants will differ, some variability is unavoidable.

*Safety Precautions:* The findings from the first 5 participants to be enrolled in either dosage group will be assessed before enrollment can continue. Details are provided in [Section 3.1.1](#). As a further precaution, alert events have been defined that will mandate extra monitoring or termination from the study in any patient in whom they are observed. Information on alert events is provided in [Section 4.5.1](#).

*Endpoints:* The endpoints are safety and acceptability. No endpoints for efficacy have been included, as bioequivalence of deferiprone DR tablets to Ferriprox IR tablets over a 24-hour period has already been demonstrated.

### **3.3 Rationale for Selection of Doses**

For Ferriprox, dosages of 75 mg/kg/day and 100 mg/kg/day represent the most common starting dose and the maximum recommended dose, respectively, of the therapeutic dose range approved for patients with systemic iron overload. The dosage groups in this study will be within either the upper half or the lower half of this range.

The Phase I studies LA58-0118 and LA60-0118, conducted in healthy volunteers, both evaluated the maximum recommended dose of deferiprone (100 mg/kg/day) without the titration that is

normally recommended for initiation of treatment in patients with iron overload. In both studies, following receipt of deferiprone DR, there were higher than expected percentages of subjects with GI events and elevated liver enzymes. It is possible that starting the dosing directly at 100 mg/kg/day with no titration may have been a factor in the occurrence of both types of events. It is also known that healthy volunteers are more adversely impacted by an iron chelator in ways that iron-overloaded patients would not be. That is, these events may prove to be less prominent in the latter since with them, deferiprone will rapidly bind to excess iron and will thus be less available for involvement in other biochemical reactions. As the maximum recommended dosage of deferiprone is essential in some patients, it is important to assess dosages at the high end of the range in the target population, with safety measures in place to ensure that participants are not placed at undue risk. In the case of liver enzymes, increases in ALT and AST are commonly observed in patients with transfusion-dependent thalassemia, irrespective of deferiprone therapy, and thus the clinical significance of any increase needs to be evaluated in individual patients based on their medical history.

Comparison of the low and high dosages will allow for assessment of a dose effect of deferiprone. In healthy volunteers, in contrast to the elevated ALT and AST levels seen at 100 mg/kg/day, no such concerns were observed in the earlier study LA45-0116, which employed a fixed dosage of 1500 mg b.i.d., the equivalent of about 20 mg/kg in an average-weight (70 kg) person. There would be no purpose in assessing a sub-therapeutic dosage in patients, but it will be of interest to see if there are fewer or less severe liver enzyme elevations in the lower dosage group.

## **4 STUDY POPULATION**

### **4.1 Number of Patients**

A total of 30 patients will be enrolled in this study, 15 in each dosing dosage group.

### **4.2 Inclusion Criteria**

Individuals will be eligible to enroll in the study if they meet **all** the following criteria:

1. Male or female aged  $\geq 18$  years.
2. Diagnosis of thalassemia syndrome, sickle cell disease, or other disorder requiring a regular regimen of red blood cell transfusions.
3. On a stable regimen ( $\geq 3$  months) of Ferriprox tablets for the treatment of systemic iron overload.
4. Absolute neutrophil count  $\geq 1.5 \times 10^9/L$  at screening.
5. A record of at least 12 measured ALT and AST levels.

6. A female volunteer must meet one of the following criteria:
  - If of childbearing potential, have a negative pregnancy test result at screening. In addition, she must:
    - a. Agree to use an effective method of contraception according to local requirements, during the study and afterwards, OR
    - b. Have undergone a tubal ligation (supporting evidence required), OR
    - c. Abstain from heterosexual intercourse, OR
    - d. Have a male sexual partner who has been sterilized (supporting evidence required)
  - Be of non-childbearing potential, defined as surgically sterile, having undergone complete hysterectomy or bilateral oophorectomy (supporting evidence required) or being in a menopausal state (at least 1 year without menses)
7. Fertile heterosexual males and/or their partners must agree to use an effective method of contraception during the study and afterwards.
8. All patients and/or their authorized legal representatives must provide signed and dated written informed consent prior to the first study intervention, and patients must be able to adhere to study restrictions, appointments, and evaluation schedules.

#### **4.3 Exclusion Criteria**

Individuals will be excluded from enrollment if they meet **any** of the following criteria:

1. Receipt of any iron chelator other than Ferriprox (i.e., combination therapy) in the last 3 months, or planning to receive it at any time during the period of the study.
2. ALT and/or AST value > 5 times the upper limit of normal (ULN) at screening
3. Active case of hepatitis B or C at screening.
4. Positive for HIV at screening.
5. A serious, unstable illness, as judged by the Investigator, during the past 3 months before screening/baseline visit including but not limited to: hepatic, renal, gastroenterologic, respiratory, cardiovascular, endocrinologic, neurologic, or immunologic disease.
6. Evidence of abnormal kidney function at screening (creatinine levels >2 x ULN).
7. Myocardial infarction, cardiac arrest or cardiac failure within 1 year before screening/baseline visit.
8. Bowel disease causing malabsorption.
9. History of allergy or sensitivity to the study product or related compounds or to other components of the formulation.

10. Receipt of any investigational products within the past 30 days or 5 half-lives (whichever is longer) preceding the first dose of study medication.
11. Participation in any investigational clinical study, other than observational, within the past 30 days; or plans to participate in such a study at any time from the day of enrollment until 30 days post-treatment in the current study.
12. History of drug or alcohol abuse within the last 6 months.
13. Presence of any medical, psychological, or psychiatric condition which in the opinion of the investigator would cause participation in the study to be unwise.
14. Pregnant, breastfeeding, or planning to become pregnant during the study period.
15. Identified as an investigator or other site staff directly affiliated with this study, or an immediate family member (spouse, parent, child, or sibling, whether biological or legally adopted) of either of the above.

#### **4.4 Enrolment Violations**

The criteria for enrolment must be followed explicitly. If there is inadvertent enrolment of patients who do not meet enrolment criteria, the investigator should consider withdrawing these individuals from the study.

#### **4.5 Patient Withdrawal**

Patients have the right to withdraw from the study at any time and for any reason without consequence to future care by the investigator or study center.

A patient may be withdrawn from the study at any time, at the discretion of the investigator, for any of the following reasons:

- Medical or safety reasons considered significant by the patient and/or the investigator
- Requirement for concomitant medication that might interfere with the evaluation of study treatment or may be contraindicated
- Receipt of a rescue medication
- Occurrence of other illnesses that might affect the patient's further participation in the study or evaluation of study treatment
- A protocol deviation that might interfere with study assessments, as judged by the investigator
- Repetitive patient non-compliance with the protocol or with instructions of the investigator
- Participation in another clinical trial at any time during the conduct of this study
- Any other situation where, in the opinion of the investigator, continuation of the study would not be in the best interest of the patient

A patient **must** be withdrawn from the study if any of the following conditions apply:

- Pregnant or planning to become pregnant (see [Section 7.1.4](#))
- A confirmed ALT or AST value  $>10 \times \text{ULN}$  (see [Sections 4.5.1.1](#) and [7.1.1.8.1](#))
- A confirmed ANC value  $< 0.5 \times 10^9$  (see [Sections 4.5.1.2](#) and [7.1.1.8.2](#))
- Occurrence of any adverse event characterized as life-threatening or disabling that is not associated with the patient's condition
- Termination of the study by the sponsor

Patients who decide to withdraw participation in the study should always be contacted, if possible, in order to ask about the reason for withdrawal, whether any adverse events (AEs) occurred, and use of concomitant medications. A withdrawn patient should return for an early termination visit and a follow-up visit. All investigational product and materials should be returned. If any AEs occurred, the investigator must attempt to follow up the outcome until resolution.

If a patient withdraws or is withdrawn before completing the study, the date and reason for the withdrawal must be entered on the source document and on the appropriate page of the electronic case report form (eCRF), and all other appropriate eCRF pages must be completed.

#### **4.5.1 Alert Events and Individual Stopping Rules**

Certain events are defined in this study as alerts, meaning that any occurrence must be carefully monitored, and in some cases may mandate withdrawal of a patient or even early termination of the study.

##### **4.5.1.1 Elevated Liver Enzymes**

A patient who reaches an ALT and/or AST value  $\geq 10 \times \text{ULN}$  at any time during the study is to be **immediately** withdrawn if he or she is additionally symptomatic and/or has any other clinically significant abnormal laboratory results. If there are no other signs of concern, a confirmatory count is to be obtained the next day. If the value is confirmed, the patient is to be withdrawn; if it is not, the patient is to be closely monitored. Details are provided in [Section 3.1.1.1](#).

##### **4.5.1.2 Neutropenia**

A sudden drop in absolute neutrophil count (ANC) is a reaction that has been associated with deferiprone treatment and is considered an adverse event of special interest. ANC values will be monitored throughout the study. For a case of mild, moderate, or severe neutropenia to be confirmed, there must be 2 consecutive counts of ANC, a maximum of 3 days apart,

that are both less than a specific value. If at any time, a patient's confirmed ANC level is found to be below  $< 1.5 \times 10^9/L$ , the investigator is to do the following:

- *Mild neutropenia:* If the confirmed ANC is  $< 1.5 \times 10^9/L$  but  $\geq 1.0 \times 10^9/L$ , continue treatment without interruption, but monitor ANC every 2 days until resolution.
- *Moderate neutropenia:* If the confirmed ANC is  $< 1.0 \times 10^9/L$  but  $\geq 0.5 \times 10^9/L$ , interrupt treatment and monitor ANC every 2 days until resolution. The patient should re-initiate treatment once the event is resolved. If ANC is still  $< 1.5 \times 10^9/L$  after 14 days, withdraw patient from the study and monitor until resolution of the event.
- *Severe neutropenia / agranulocytosis:* If a single ANC is  $< 0.5 \times 10^9/L$ , immediately interrupt treatment without waiting for confirmation of the count and obtain a second measurement the following day. If the second ANC is still  $< 0.5 \times 10^9/L$ , permanently withdraw the patient from the study and follow the procedures for the management of agranulocytosis.

Details on the management of each category of neutropenia are provided in [Section 7.1.1.8.2](#).

#### **4.5.1.3 Infection**

If a patient reports any symptoms indicative of infection such as fever, sore throat, or flu-like symptoms, interrupt treatment immediately and obtain an ANC measurement, and monitor ANC more frequently; every 2 days if it is below  $< 1.5 \times 10^9/L$  but  $\geq 0.5 \times 10^9/L$ . Therapy can be re-initiated once all symptoms have been resolved and it is deemed safe by the investigator. (If ANC is found to be above  $1.5 \times 10^9/L$ , treatment can be continued if the investigator assesses the patient and considers continuation to be safe. Treatment should be interrupted in any case of fever of  $38.5^\circ\text{C}$  or greater.)

#### **4.5.2 Follow-up of Patient Withdrawal Due to Pregnancy**

All females of childbearing potential must have a negative serum pregnancy test prior to study entry and prior to first administration of the study drug, and must agree to use an approved method of contraception (as defined in inclusion criterion #5) throughout the course of the trial. If a patient does become pregnant, the investigator must do the following upon becoming aware of the pregnancy:

- Ensure that the study medication is stopped immediately
- Inform the sponsor via the pregnancy report form
- With the patient's consent, follow the pregnancy closely, and provide reports to the sponsor until delivery or other resolution

A male patient must inform the investigator if his female partner becomes pregnant during the trial or within 1 month following the last dose of study medication. As with the pregnancy of a female subject, the site must inform the sponsor and, if the partner consents, follow the pregnancy and provide the sponsor with a report on its outcome.

#### **4.5.3 Replacement of Patients Who Withdraw**

Patients who are withdrawn from the study will not be replaced.

#### **4.6 Prior and Concomitant Therapies**

To be considered for enrollment, patients cannot be taking any iron chelator other than Ferriprox. Those who are on a combination regimen of Ferriprox and another product are not eligible.

In addition, during the trial, they may not take any other investigational product, or any drugs that are known to cause agranulocytosis. Medications that are being taken on a stable regimen and that are considered necessary for the subject's welfare may continue to be taken, at the discretion of the investigator. All medications (including study product, herbal medications, and over-the-counter medications) and nutritional supplements taken from 3 months prior to screening up to the end of the study (Day 28 or early termination) must be reviewed by the investigator and recorded in the source document and in the appropriate section of the eCRF.

#### **4.7 Rescue Medication**

Patients will be assigned to Group A or Group B based on the total daily dosage of Ferriprox they have been taking for the last 3 months (i.e., closer to 75 mg/kg/day or closer to 100 mg/kg/day) and must remain on their assigned dosage for the duration of the study. If it is determined during the study that a change in dosage or the addition of another chelator is required to control iron load, that patient will be withdrawn from the trial.

### **5 STUDY PROCEDURES**

The procedures and assessments to be conducted at each study visit are shown in [Table 5.1](#).

**Table 5.1 Table of study procedures**

Study Procedure	Screening Day -14 to -1	Baseline Day 0	Day 3 (±1 day)	Day 7 (±1 day)	Day 14 (±2 days)	Day 21 (±2 days)	Day 28 (±2 days) or early termination 
Informed consent	X						
Demography	X						
Medical history 	X						
Medication history	X	X					
Eligibility criteria	X	V					
Biochemistry 	X		X	X	X	X	X
Hematology 	X	X		X	X	X	X
Coagulation 	X						X
Serology 	X						
Urinalysis 	X						X
Physical examination 	X						X
Vital signs	X						X
Serum pregnancy test 	X						X
Dispense study medication		X					
Dosing	Twice-daily from Day 1 to Day 28						
Collect study medication containers							X
Treatment compliance							X
Medical events	X	X					
Adverse events/ serious adverse events	Throughout the study						
Concomitant medications	Throughout the study						
Acceptability questionnaire							X

V: Verify

1. If deemed necessary, patients with ongoing adverse events may be asked after the last dose to provide further blood samples until resolution
2. Medical history is to include a record of at least 10 measured ALT and AST levels
3. Biochemistry: Total protein, gamma-glutamyl transferase (GGT), lactate dehydrogenase (LDH), sodium, potassium, chloride, glucose, bilirubin (total, direct, and indirect), alanine aminotransferase (ALT), aspartate aminotransferase (AST), albumin, blood urea nitrogen, calcium, creatinine, uric acid, alkaline phosphatase, amylase, serum ferritin, and blood iron
4. Hematology: Hemoglobin, total WBC count, ANC, MCV, and platelet count
5. Coagulation: Prothrombin Time (PT), Partial Thromboplastin Time (PTT), and International Normalized Ratio (INR)
6. Serology: HIV Ag/Ab Combo, hepatitis B (HBsAg (B)), and hepatitis C (anti-HCV (C))
7. Urinalysis: Color, appearance, specific gravity, pH, leukocyte, protein, glucose, ketones, bilirubin, blood, nitrite, urobilinogen. Microscopic examination must be performed if dipstick test is outside the reference range for leukocyte, blood, nitrite or protein. (Note: for patients with sickle cell disease, samples are to be sent for microscopy if there is blood in the urine or three or more “plus signs” for protein.)
8. At screening, a full physical examination will be performed, including measurement of weight. At Day 28 (or early termination), only a symptom-oriented examination will be performed.
9. Pregnancy testing (females only): Beta-HCG qualitative serum pregnancy test

## 5.1 Visit Procedures

Details on the procedures to be carried out at each study day are provided below. For details of the safety assessments, see [Section 7.1](#).

**Note:** The procedures at screening, baseline, and Day 28 must be conducted at the study site. The procedures on all other study days may be handled via a telephone call (for collection of information on adverse events and concomitant medications) and at a local laboratory (for collection of blood samples for safety assessments). If a patient chooses to go to a local laboratory, the same one must be used throughout the entire study.

### **Screening Visit (Day -14 to Day -1)**

- Explain the study to the prospective participant, and obtain written informed consent
- Collect demographic information
- Collect medical history
- Collect history of the last 12 or more ALT and AST results
- Collect information on prior and concomitant medications including current chelation therapy
- Collect blood samples for assessment of the following:
  - Biochemistry
  - Hematology
  - Coagulation
  - Serology
  - Pregnancy testing (women of childbearing potential only)
- Collect a urine sample for urinalysis. Microscopic examination must be performed if dipstick test is outside the reference range for leukocyte, blood, nitrite or protein. (Note: for patients with sickle cell disease, samples are to be sent for microscopy if there is blood in the urine or three or more “plus signs” for protein.)
- Perform a physical examination (to be completed by the principal investigator or a qualified delegate), including weight
- Measure vital signs (heart rate, blood pressure, and body temperature)
- Record any medical events that have occurred after the consent form was signed

Patients who are found to be eligible will complete the procedures below.

### **Baseline Visit (Day 0)**

- Verify that the patient has met all inclusion/exclusion criteria
- Collect information on prior and concomitant medications
- Collect a blood sample for hematology
- Collect any medical events that have occurred since the previous visit
- Conduct contraceptive counseling if applicable
- Dispense an appropriate supply of deferiprone DR tablets at the specified dosage (see [Section 6.1.1](#)), along with instructions on how to take them. The first dose is to be taken the next day, in the morning. Patients are to be instructed to always take the medication with food.
- Provide patient with an emergency card with contact information, and explain that it is to be carried at all times
- Instruct patient to do the following:
  - Keep a record of all dosing, any concomitant medications that are taken, and any health problems that occur
  - In the event of any symptoms indicative of infection such as fever, sore throat, or flu-like symptoms, immediately interrupt therapy and contact the clinic
  - At the final visit, bring back the completed notes plus all medication containers, whether empty, partly used, or unopened
  - In the event of a decision to withdraw from the study before completion, return to the clinic for an Early Termination Visit as soon as possible, and no later than one month following the last dose of study medication

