Diagnosis and main criteria for inclusion:	
Main inclusion criteria
 
 
• Male or female aged <math>\geq 18</math> years
 
• Diagnosis of thalassemia syndrome, sickle cell disease, or other disorder requiring a regular regimen of red blood cell transfusions
 
• On a stable regimen (<math>\geq 3</math> months) of Ferriprox tablets for the treatment of systemic iron overload
 
• A record of at least the last 12 measured ALT and AST levels prior to baseline
 
 
Main exclusion criteria
 
 
• ALT and/or AST value <math>> 5 \times</math> ULN at screening
 
• Active case of hepatitis B or C at screening
 
	
Investigational product:	
Product: Deferiprone delayed release (DR) 1000 mg tablets
 
Dose: All patients will receive deferiprone DR at approximately the same total daily dosage at which they were taking Ferriprox (Group A: closer to 75 mg/kg/day; Group B: closer to 100 mg/kg/day), approximately 12 hours apart, rounded to the nearest 500 mg half-tablet
 
Mode of administration: Oral
	
Schedule of treatment and specimen collection:	
Schedule of Treatment
 
Patients will receive 28 days of b.i.d. dosing with deferiprone DR tablets.
 
 
• Biochemistry: Screening and Days 3, 7, 14, 21, and 28
 
• Hematology: Screening, baseline, and Days 7, 14, 21, and 28
 
• Coagulation: Screening and Day 28
 
• Serology: Screening
 
	

Name of Sponsor: ApoPharma Inc.	Individual Study Table	(For National
Name of Finished Product: Deferiprone delayed release tablet	Referring to Part of the	Authority Use Only)
Name of Active Ingredient: 3-hydroxy-1,2-dimethylpyridin-4-one	Dossier Volume: Page:	

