## 1.2 Rationale

According to pharmacokinetic bioequivalence criteria, adverse events that depend on  $C_{max}$  and/or AUC would be expected to be the same for two formulations that provide equivalent  $C_{max}$  and AUC over a 24-hour period. While transient liver enzyme elevations are a known adverse event at initiation of therapy with Ferriprox IR, particular attention will be paid to this effect in the current study given the rate of elevated liver enzymes seen in the Phase I study. While the reason for that happening is unclear, it is hypothesized that this effect will be less prominent in iron-overloaded individuals, since with them, unlike in healthy volunteers, deferiprone will rapidly bind to excess iron and will thus be less available for involvement in other biochemical reactions.

Previous clinical trials of deferiprone IR in patients with thalassemia have shown that ALT values in individual patients fluctuate, with declines from baseline of up to 369 U/L and increases from baseline of up to 564 U/L. ALT levels of at least twice the upper limit of the reference range have been observed in up to 60% of patients treated with deferiprone. In the majority of these patients, the increase is asymptomatic and returns to baseline levels without discontinuation or dose reduction of deferiprone. In ApoPharma clinical trials, elevations of liver enzymes led to discontinuation of deferiprone therapy in only 5 of 889 patients; 4 (0.4%) due to increased serum ALT levels and 1 (0.1%) due to an increase in both ALT and AST.

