Screening will be conducted within 14 days prior to the start of dosing, and with the exception of hematology, laboratory results obtained at that time will be treated as the baseline values. Blood samples will be collected for the assessment of biochemistry (screening and Days 3, 7, 14, 21, and 28), hematology (screening, baseline, and Days 7, 14, 21, and 28), serology (screening only), and other safety parameters (screening and Day 28); and urine samples will be collected for urinalysis (screening and Day 28). For the Day 3, 7, 14, and 21 samples, patients may choose to visit a local laboratory instead of the study site; if this is done, they must use the same laboratory throughout the entire study. If deemed necessary, patients with ongoing adverse events may be asked after the last dose to provide further blood samples for up to 30 days or until resolution. On Day 28, patients will be asked for their views on the acceptability of the delayed release formulation vs. the immediate release (Ferriprox) tablets. Any patient who withdraws before completing treatment will be requested to return for an Early Termination visit, at which time the procedures scheduled for the Day 28 visit will be conducted.

As this will be the first time that deferiprone DR is administered to patients with iron overload, as a precaution, enrollment will be conducted progressively in small groups, and safety results will be reviewed following the enrollment of a limited number of patients. Decisions regarding continuation will be based on the findings. Details are provided in [Section 3.1.1](#).

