**Notes:**

- With the exception of hematology, laboratory results obtained at screening will be treated as the baseline values.
- There will be a window of  $\pm 1$  day for assessments done at Days 3 and 7, and of  $\pm 2$  days for assessments done at Days 14, 21, and 28.
- The investigator may increase the frequency of safety evaluations if deemed appropriate for assessment of any clinically significant adverse event. In the case of increases in liver enzymes that meet the criteria for being considered a safety concern, the patient is to be followed until resolution of the event, beyond Day 28 if necessary.
- If a patient withdraws from the study, the End of Study procedures are to be performed at an early termination visit.

Investigators must document their review of each laboratory report by signing or initialing and dating it. Any laboratory values that fall outside a clinically accepted range, or values

that differ significantly from previous values, must be marked by the investigator as either “CS” (clinically significant) or “NCS” (not clinically significant). Any that are marked as CS must be further explained and documented as an AE.

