### 9.1 Endpoints

#### 9.1.1 Primary Endpoint

The primary endpoint is the incidence of any post-dose occurrence of increases in ALT and/or ALT levels that meet one of the criteria for being considered a safety concern. The safety criteria are:

- For a patient whose baseline level is within the normal range, the criterion will be reaching a value of 5 times the ULN during the study.
- For a patient whose baseline level is above the ULN, the criterion will be reaching a value of 5 times the baseline value during the study or  $>10 \times$  ULN.

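### ALT and AST are not measured at Day 0 although blood is drawn then, so the primary endpoint threshold rests on one screening value up to about two weeks old: a stated choice that is cheap to improve

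*Combined protocol and SAP*

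**What the plan says.** ALT and AST belong to the biochemistry panel. The synopsis schedules "Biochemistry: Screening and Days 3, 7, 14, 21, and 28", whereas for blood counts it has "Hematology: Screening, baseline, and Days 7, 14, 21, and 28". Section 5.1 matches this: at the Day 0 site visit the only sample is "Collect a blood sample for hematology".

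Section 3.1 sets the timing, "Screening will be conducted within 14 days prior to the start of dosing", and the baseline rule, "with the exception of hematology, laboratory results obtained at that time will be treated as the baseline values". The synopsis and the notes to Section 7.1.2 repeat that rule. Table 5.1 places screening at Day -14 to -1, and the first dose is taken on the morning after Day 0.

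Section 9.1.1 uses the baseline twice. It decides whether the rule for normal or for raised baselines applies, and for raised baselines "the criterion will be reaching a value of 5 times the baseline value during the study", with an alternative limb at 10 x ULN. Section 3.1.1.1 applies the same criteria to 24-hour reporting, and Section 3.1.1.2 counts patients who meet them (2 of 5, then 4 of 10) in the enrollment reviews.

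**The concern.** The baseline is part of the definition of the primary endpoint, not just a descriptive variable. A chance high screening value raises the patient's threshold and can hide an event; a chance low value lowers it and can create one. Sections 1.2 and 3.1.1.1 both describe these enzymes as fluctuating in this population. With no control arm, the pre-switch level is the only within-study comparator for the move from the immediate release to the delayed release tablet.

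The groups are small. One patient of 15 is 1/15 = 6.7 percentage points of incidence, and the Clopper-Pearson 95% interval goes from 0-21.8% for no events to 0.2-31.9% for one. In an enrollment review of 5 patients, one misclassified patient can decide whether the count of 2 is reached. Blood is already being drawn at Day 0, and a pre-dose sample cannot be recovered once dosing has begun.

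**Working it through.** The plan gives no figure to reproduce: Section 9.2 states that no power calculation can be done, and no within-patient variance is reported.

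**Step 1: threshold as a function of baseline.** Let b be the baseline in multiples of ULN, and read the raised-baseline rule as met when either limb is reached. Then T(b) = 5 if b ≤ 1, 5b if 1 < b < 2, and 10 if b ≥ 2. For example, b = 1.2 gives 6, b = 1.5 gives 7.5, and b = 3 gives 10. Only baselines between 1 and 2 x ULN scale the threshold.

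**Step 2: threshold error.** Assumptions, none from the documents: log b is normal around the log of the usual level μ with within-patient SD σ = 0.2 to 0.5, and samples are independent. A geometric mean of k values has log-SD q = σ/√k. The error is counted when T(b) differs from T(μ) by more than 20%:

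- μ = 1.0: only b > 1.2 counts, so P = 1 − Φ(ln 1.2 / q).
- μ = 1.5: b < 1.2 or b > 1.8, so P = Φ(ln 0.8 / q) + 1 − Φ(ln 1.2 / q).
- μ = 2.0: only b < 1.6, so P = Φ(ln 0.8 / q).
- μ = 3.0: only b < 1.6, so P = Φ(ln(1.6/3) / q).

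Worked case, μ = 1.5 and σ = 0.2: one value gives 13.2% + 18.1% = 31.3%; two values (q = 0.141) give 5.7% + 9.9% = 15.6%.

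Screening values above 5 x ULN are excluded (Section 4.3), which changes only the σ = 0.5 end noticeably. For μ = 2.0 and one value it gives 32.8% / Φ(ln 2.5 / 0.5) = 32.8% / 0.967 = 33.9%. A simulation of the same rule with that exclusion gives:

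| Usual level (x ULN) | One value, σ 0.2 to 0.5 | Mean of two, σ 0.2 to 0.5 |
|---|---|---|
| 1.0 | 18%-36% | 10%-30% |
| 1.5 | 31%-68% | 16%-56% |
| 2.0 | 13%-34% | 6%-27% |
| 3.0 | 0.1%-12% | at most 5% |

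For a usual level of 0.6 x ULN, one value gives 0%-8%.

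**Step 3: events rather than thresholds.** One enzyme is simulated over the five post-dose visits. An event is misclassified when its status under T(b) differs from its status under T(μ). At μ = 1.5:

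- True 3-fold rise: about 12%-28% with one value and 7%-24% with two. At any given σ the reduction is about 3 to 5 percentage points.
- No drug effect: 0%-1.2% with one value and 0%-1.0% with two.

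If all 15 patients in a group sat at 1.5 x ULN and had a 3-fold rise, the second value would correct about 0.5 to 0.8 of a patient.

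**Step 4: correlation.** If the two samples have correlation ρ, q = σ√((1 + ρ)/2): 0.71σ at ρ = 0, 0.87σ at ρ = 0.5, and σ (no gain) at ρ = 1. Screening may fall on Day -1, so two samples a day apart are possible and the gains above are upper values.

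**The case against.** The screening baseline is declared openly and identically wherever it appears. Patients must have been on a stable regimen for at least 3 months, so no planned treatment change falls between screening and Day 0. A single baseline within two weeks is defensible. This stands: the point is a possible improvement and not a contradiction.

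A reader might take Section 1.2, with ALT "declines from baseline of up to 369 U/L and increases from baseline of up to 564 U/L", as proof of large swings within two weeks. It is not. Those are extremes from earlier trials over an unspecified follow-up, and no within-patient SD can be derived from them. The range 0.2-0.5 remains an assumption.

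A reader might also take 31%-68% as the share of trial patients with a misplaced threshold, or of events miscounted. The documents give no distribution of baseline levels, so the figure describes only a patient usually at 1.5 x ULN, close to the most sensitive point. Step 3 shows that the gain in events is far smaller.

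Finally, Section 5.1 already collects the last 12 or more ALT and AST results, and Section 1.2 says the past record will be considered, yet the criteria do not use it. Under an assumed log-SD of 0.4 at 1.5 x ULN, the 5th-95th percentile range of the threshold is 5.0-10.0 with one value, still 5.0-10.0 with two, and 6.0-9.4 with the median of 13 (12 past values plus screening). So the history could narrow the threshold more than one Day 0 sample. That qualifies the benefit of the Day 0 sample without removing the case for it: it is the last value before the switch.

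**Conclusion.** The point holds as a low-cost design improvement. The facts are certain: ALT and AST are not taken at Day 0, blood is drawn then anyway, and one screening value selects and scales the primary endpoint threshold between 5 and 10 x ULN. A second value reduces threshold error mainly at usual levels of about 1-2 x ULN and does not remove it. The event-level gain is modest, about 3-5 percentage points at 1.5 x ULN after a true 3-fold rise and close to nothing without a drug effect. All percentages rest on the assumed log-SD and on independent samples; correlated samples would shrink the gain. The documents do not support the stronger conclusion that the baseline rule is an error, or that it would seriously distort the primary result.

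**What to change.** - Add ALT and AST to the Day 0 draw in Table 5.1, Section 5.1, Section 7.1.2 and the synopsis schedule.
- Prespecify, for each enzyme, the baseline as the geometric mean of the screening and Day 0 values, in multiples of ULN.
- Amend the baseline statements in Section 3.1, Section 7.1.2 and the synopsis so that Sections 3.1.1.1 and 9.1.1 use this same baseline for safety-concern reporting, enrollment-review counts and the primary endpoint. If only the analysis baseline changed, a patient could count in an enrollment review but not in the endpoint, or the reverse.
- Keep eligibility on the screening value, so dispensing need not wait.

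Cost: two routine analytes at an existing venepuncture in 30 patients, no new visit, and one extra result that must be available before the first post-dose assessment at Day 3.
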